## 9.2 SAMPLE SIZE DETERMINATION

The sample size (N=30 in 6 months) was chosen to demonstrate feasibility to enroll 180 women in 36 months at our site during a larger multi-site trial and to successfully complete follow-up.

## 9.3 POPULATIONS FOR ANALYSES

The following datasets will be utilized for analysis:

- Intention-to-Treat Analysis Dataset: All participants randomized with known outcomes per the 8 week follow up survey.
- Per-Protocol Analysis Dataset: Participants who reported taking their assigned POP throughout the study period and reported follow up data on the 8 week survey.

## 9.4 STATISTICAL ANALYSES

### 9.4.1 GENERAL APPROACH

### 9.4.2 ANALYSIS OF THE PRIMARY EFFICACY ENDPOINT(S)

A survival analysis will be conducted to to assess time spent exclusively breastfeeding.

### 9.4.3 ANALYSIS OF THE SECONDARY ENDPOINT(S)

Proportions will be compared using chi-square tests. ANOVAs will be used to calculate means for analysis using all 3 groups and t-tests for any pairwise comparisons.

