## 3 OBJECTIVES AND ENDPOINTS

Aim	Variable	Description	Source
Maternal Outcomes			
1a	Breastfeeding	Exclusive breastfeeding : own mother's milk via breast or bottle. Predominant breastfeeding : greater than 75% of the infant's diet is their own mother's milk; the remainder of the diet is formula, donated milk, or other supplemental foods Mixed Breastfeeding : 25-75% or more of the infant's diet is their own mother's milk Predominantly supplementing : <25% diet is breastmilk No breastfeeding : infant is not consuming own mother's milk	End of weeks 2-8
1a	Supplementation type	Donated breastmilk, formula, other milks (cow, plant-based, nut), juice, water, cereal, other foods	End of weeks 2-8
1b	Progestin-only pill use	Any use, timing of initiation of POP use (assigned), type of POP (assigned), number of missed pills	End of weeks 2-8.
1b.	Contraception use	Sterilization (male and female), intrauterine devices, subdermal implants, oral contraceptives (combined), condoms (male and female), injectables, emergency contraceptive pills, patches, diaphragms, sponges, cervical caps, spermicidal agents, vaginal rings, withdrawal, fertility awareness, abstinence, and LAM	4 and 8 weeks
	Vaginal bleeding	Number of days of any bleeding and spotting in last month	Estimated at 4 and 8 weeks
	Satisfaction with contraception	Satisfied with method, would recommend method to a friend	4 and 8 weeks
	Pregnancy	Self-reported new pregnancy, pregnancy intendedness, whether planning to continue the pregnancy or not, and pregnancy outcome: continued, terminated, pregnancy loss	4 and 8 weeks
Milk Outcomes			
2	Composition of breastmilk	Fat, protein, carbohydrate (including oligosaccharide) content of milk	4-week breastmilk sample
	Maternal perception of adequate milk supply	Hill and Humenick Lactation Scale	End of weeks 2-8
Infant Outcomes			
3	Change in infant growth	Weight, length, and head circumference	Change between baseline and 4 weeks

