## 6 STUDY INTERVENTION

### 6.1 STUDY INTERVENTION

Group 1: Initiation of d-POPs 120-160 hours after delivery (N=10)

Group 2: Initiation of n-POPs 120-160 hours after delivery (N=10)

Group 3: Initiation of d-POPs 4 weeks after delivery (N=10) [placebo starting 120-160 hours, continuing for 28 days]

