## 9 STATISTICAL CONSIDERATIONS

### 9.1 STATISTICAL HYPOTHESES

Comparisons will be made between groups 1 and 2 to assess differences in outcomes by type of progestin used, and between groups 1 and 3 to assess differences in outcomes by timing of progestin initiation. The primary outcome is the proportion of women exclusively breastfeeding at 8 weeks postpartum. Differences in baseline demographic characteristics and in variables between groups will be assessed using  $\chi^2$ , Fisher exact, or t-tests as appropriate.

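### Section 3 grades infant feeding in five ordered levels, but the plan names no ordinal method and does not say which test applies to the scale

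*Combined protocol and SAP*

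**What the plan says.** Section 3 lists the Aim 1a breastfeeding variable at the end of weeks 2-8 in five levels, defined by how much of the infant's diet is the mother's own milk: exclusive, predominant, mixed, predominantly supplementing and none. Predominant is "greater than 75% of the infant's diet is their own mother's milk"; mixed is "25-75% or more of the infant's diet is their own mother's milk".

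The Section 1.1 synopsis makes supplementation over 8 weeks part of Aim 1a. The tests on offer are these:

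- Section 9.4.3, secondary endpoints: "Proportions will be compared using chi-square tests", with ANOVA and t-tests for means.
- Section 9.1, baseline characteristics and variables between groups: chi-square, "Fisher exact, or t-tests as appropriate".
- Section 9.4.2, primary endpoint: "A survival analysis will be conducted to to assess time spent exclusively breastfeeding".

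Section 9.1 also states that "The primary outcome is the proportion of women exclusively breastfeeding at 8 weeks postpartum". On contrasts it says "Comparisons will be made between groups 1 and 2 to assess differences in outcomes by type of progestin used", and it compares Groups 1 and 3 for timing. Section 6.1 gives 10 women per group.

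No rank test or ordinal model appears in the document, and Section 9.4.3 does not mention the five-level scale.

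**The concern.** The survival analysis in Section 9.4.2 uses only whether, and when, exclusive feeding ended. The four lower levels, which record how far supplementation went, have no named analysis. An analyst following the plan would probably turn to its only categorical rule.

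Pearson chi-square across five levels gives the same answer however the columns are ordered. A move from exclusive to predominant counts no differently from a move from exclusive to none. With 10 per arm the table is also too sparse for the chi-square approximation.

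A graded move toward supplementation is one of the effects the trial is looking for, and Section 4.1 hypothesises no clinically meaningful effect on supplementation. A conservative test that ignores direction handles that kind of shift poorly. Section 2.2 says the pilot is meant to inform a larger trial, and a p-value from a sparse 2x5 table offers little for that.

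**Working it through.** **The plan's own figure.** Section 9.2: 180 women / 36 months = 5 per month; 5 x 6 months = 30 = 3 arms x 10. This reproduces. It is a feasibility number, and no power is stated.

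**Inputs from the plan.** Five ordered levels (Section 3); 10 per arm (Section 6.1); pairwise contrasts 1 v 2 and 1 v 3 (Section 9.1).

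**Assumptions, because the plan gives none.** Two-sided alpha 0.05; all 10 per arm analysed; reference-arm distributions over the five levels, best to worst:
- 40% exclusive: .40, .25, .15, .10, .10
- 50%: .50, .20, .15, .05, .10
- 60%: .60, .15, .10, .05, .10
- 70%: .70, .12, .08, .05, .05
- 80%: .80, .10, .05, .03, .02
- uniform: .20 in each level

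**Effect model.** Proportional odds: each cumulative odds in the reference arm is divided by a common odds ratio (OR) of 2, 3, 5 or 10. Example: 60% exclusive has odds 0.6/0.4 = 1.5; at OR 3 the odds are 0.5, so 0.5/1.5 = 33% are exclusive.

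**Tests.**
- Pearson chi-square: sum of (O - E)^2/E, empty columns dropped. With all five columns filled, df = (2-1)(5-1) = 4.
- Wilcoxon rank-sum with mid-ranks: z = (W - n(N+1)/2)/sqrt(V), where V = (nm/12)[(N+1) - sum(t^3 - t)/(N(N-1))] and t is the number tied at each level.
- On exclusive yes/no: uncorrected 2x2 chi-square, and Fisher.

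**Sparsity.** Under no effect with 60% exclusive, expected counts per arm are 10 x (.60, .15, .10, .05, .10) = 6, 1.5, 1, 0.5, 1. Four of the five columns are below 5.

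**Simulated rejection rates**, 10 v 10, 5,000 trials per setting (simulation standard error at most sqrt(0.25/5000) = 0.007; ratios are from unrounded values):

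| Exclusive in reference arm | OR | Chi-square, 5 levels | Rank test | Ratio | 2x2 chi-square | Fisher 2x2 |
|---|---|---|---|---|---|---|
| 40% | 1 | 0.028 | 0.053 | - | 0.046 | 0.014 |
| 40% | 3 | 0.114 | 0.258 | 0.44 | 0.150 | 0.071 |
| 40% | 5 | 0.247 | 0.480 | 0.52 | 0.246 | 0.126 |
| 60% | 1 | 0.015 | 0.049 | - | 0.040 | 0.014 |
| 60% | 3 | 0.107 | 0.241 | 0.45 | 0.194 | 0.089 |
| 60% | 5 | 0.248 | 0.463 | 0.54 | 0.370 | 0.208 |
| 70% | 1 | 0.012 | 0.053 | - | 0.040 | 0.013 |
| 70% | 3 | 0.080 | 0.227 | 0.35 | 0.194 | 0.090 |
| 70% | 5 | 0.202 | 0.448 | 0.45 | 0.382 | 0.221 |
| 80% | 1 | 0.007 | 0.040 | - | 0.032 | 0.007 |
| 80% | 3 | 0.052 | 0.201 | 0.26 | 0.164 | 0.079 |
| 80% | 5 | 0.144 | 0.395 | 0.36 | 0.341 | 0.192 |

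Across all six distributions and OR 2 to 10 the ratio runs from 0.23 (80% exclusive, OR 2) to 0.70 (60%, OR 10). At OR 3-5 with 40-60% exclusive it is 0.44-0.54. Under no effect the five-level chi-square rejects 0.7-3.2% of the time and the rank test 4.0-5.3%.

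**How much collapsing recovers at OR 5**, as (2x2 - five-level)/(rank - five-level):
- 40%: (0.246 - 0.247)/(0.480 - 0.247), about 0
- 60%: (0.370 - 0.248)/(0.463 - 0.248) = 0.122/0.215 = 0.57
- 70%: (0.382 - 0.202)/(0.448 - 0.202) = 0.180/0.246 = 0.73

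A separate run of 4,000 trials at 55% exclusive gave 0.35 (2x2), 0.24 (five-level) and 0.45 (rank): 0.11/0.21 = 0.52.

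**Shifts that are not proportional** (five-level chi-square v rank test):
- 70% to 30% exclusive, all moving to predominant: 0.369 v 0.288, ratio 1.28
- 60% to 30% exclusive, all moving to predominant: 0.199 v 0.150, ratio 1.33
- 70% to 30% exclusive, all moving to none: 0.396 v 0.575, ratio 0.69
- both ends moving toward the middle (.40, .10, .10, .10, .30 to .10, .40, .30, .10, .10): 0.409 v 0.067

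**The case against.** Section 9.4.3 never assigns chi-square to the feeding scale. The plan has other proportions for that sentence to cover: pill use at 8 weeks, type of supplement (which is nominal), contraceptive method and satisfaction. A reader might infer that the plan commits to chi-square on the five levels, but the text does not say so. This stands. What remains is that the scale has no named analysis and that the only categorical tests available ignore its order.

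A reader might also infer that collapsing to exclusive yes/no cannot recover the lost power. That is a fair description of Fisher's test, which stays well below the rank test throughout. It is not true of the uncorrected 2x2 chi-square, which recovers about half or more of the loss at OR 5 with 55-70% exclusive and nothing at 40%.

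The proportional-odds pattern favours a rank test. Women enrolled because they intend to breastfeed exclusively (Section 5.1) might plausibly just begin some supplementation, and for that pattern chi-square has the higher power. This also stands, and it rules out any general claim that chi-square is the test least able to detect harm.

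Finally, N = 30 was chosen for feasibility, and the primary analysis does not use this scale. This limits the consequence but does not remove the gap, which can be closed by wording alone.

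**Conclusion.** The point holds in limited form. The plan collects an ordered outcome for a stated aim and names no method that uses the order. If its categorical rule is applied to the five levels at 10 per arm, the test is conservative (about 1-3% rejection under no effect). Under a uniform proportional-odds shift it has roughly 0.2 to 0.7 of a rank test's power.

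A figure of about half describes the middle of that range. It rests on assumed distributions, effect sizes, alpha and complete follow-up, none of which the plan supplies, and it reverses for shifts confined to the top two levels.

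A reader might infer that changing the test would let the trial support or refute its no-effect hypothesis. It would not: the rank test has power of only about 0.10-0.13 at OR 2 and 0.20-0.26 at OR 3. The gain is better use of data already being collected, and an estimate that helps plan the larger trial. The issue is worth correcting but modest in consequence.

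**What to change.** 1. In Section 3, make the feeding levels mutually exclusive before anything is ranked. As written, an infant receiving 80% mother's milk fits both predominant and mixed.
2. In Section 9.4.3, name the ordered feeding category at week 8 as an outcome. Compare it for Groups 1 v 2 and 1 v 3 by an exact or permutation Wilcoxon rank-sum test. Add week 4 for 1 v 3, because under Section 6.1 Group 3 is then still on placebo.
3. Report the probability that an infant in one arm receives more mother's milk than an infant in the other, with a 95% interval, and state how ties count (for example, as one half). Ties will be common: with 60% exclusive in both arms the chance of a tie is .36 + .0225 + .01 + .0025 + .01 = 0.405.
4. Keep the table of categories by arm as description.

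The cost is SAP wording; no new data are needed. The drawbacks are an effect measure less familiar than a difference in proportions, and lower power than chi-square if the shift stays within the top two levels or has no single direction. The rank-test figures above use the tie-corrected normal approximation; the exact version was not simulated and may be slightly more conservative.

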### 9.4.4 SAFETY ANALYSES

AEs and SAEs will be recorded by the study team when they become aware. Adverse events leading to premature discontinuation from the study intervention and serious treatment-emergent AEs will be presented in a table.

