## 1 PROTOCOL SUMMARY

### 1.1 SYNOPSIS

Title:	Postpartum progestin-only pill use and breastfeeding study
Study Description:	This study will assess the impact of early initiation (less than one week postpartum) and delayed initiation (4 weeks postpartum) of two types of progestin-only contraceptive pills on maternal, breastmilk, and infant outcomes. This is a placebo-controlled randomized controlled trial enrolling dyads of mothers and their newborn babies. We will explore if the type and timing of initiation of pills is acceptable to the user with minimal side effects, impacts the supply or composition of breastmilk, and/or affects infant growth.
Aims:	Specific Aim: To determine whether the type of progestin used (drospirenone in drospirenone-containing progestin-only pills (d-POPs) vs. norethindrone in norethindrone-containing progestin-only pills (n-POPs)) or the timing of progestin initiation (early vs. delayed) affects: Aim 1a Maternal: the duration of exclusive breastfeeding continuation or the rates and types of breastfeeding supplementation over 8 weeks postpartum. Aim 1b Maternal: the proportion of mothers using progestin-only pills at 8 weeks postpartum. Aim 2 Milk: the composition of breastmilk (fat, protein, carbohydrates) at 4 weeks postpartum. Aim 3 Infant: infant growth (weight, length, and head circumference) from birth to 4 weeks.
Study Population:	Postpartum women who delivered an infant within the previous 7 days
Description of Sites	University of California, San Diego (UCSD)
Enrolling Participants:	
Study Duration:	1 year
Participant Duration:	8 weeks

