#### **Randomization:**

A licensed medical provider on the clinical care team will review eligibility for the method and instruct patients on use of POPs prior to discharge from the hospital and will approve a prescription for both POPs. Participants will then be randomized to (1) early d-POPs to be initiated at 120-168 hours (5-7 days) after delivery, (2) early n-POPs to be initiated at 120-168 hours after delivery, or (3) placebo for 28 days followed by d-POPs initiated at 4 weeks (28-35 days) after delivery, at a 1:1:1 ratio (Figure 2). Study staff will then provide participants with written and verbal instructions about when to initiate the method and to take the study medications in the order dispensed. Participants, care providers, and research staff will be blinded to group assignment. Participants will be instructed on lactational

amenorrhea method (LAM), a highly effective form of contraception, and will be counseled that if they no longer meet criteria for LAM, then they may be at risk for unintended pregnancy between days 28 and 33 and should use condoms or abstain from intercourse during that time. Before day 28, the CDC Selected Practice Recommendations state that a provider can be “reasonably certain that woman is not pregnant” regardless of LAM use and after day 33 all study drugs will be effective contraception regardless of group assignment.

The research team will dispense two 28-day pill packs containing either d-POPs, n-POPs, or one placebo and one d-POPs, as determined by the randomization scheme, and labeled 1st and 2nd. For participants in group 3, the first pack will contain only placebo to facilitate delayed initiation while ensuring blinding. D-POP packs will include 24 active and 4 placebo tablets per month, and n-POP packs will include 28 active tablets, packaged in order of daily use. All d-POP, n-POP, and placebo tablets will be encapsulated by the research pharmacies to have an identical appearance.

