**Figure 2: Outcome Evaluation Study Design**

**Surveys:**

Investigators will send participants hyperlinks via 5 text messages weekly at the end of weeks 2, 3, 5, 6, and 7 PP. Hyperlinks will lead to a brief questionnaire that participants can complete through a smartphone or tablet. Participants will complete a tablet-based survey in person at their 4 week visit. Participants will receive an emailed hyperlink at the end of week 8 which will lead to a longer questionnaire. A telephone survey will be available as an alternative to the digital questionnaires if desired. Survey questions will address continuation of and satisfaction with breastfeeding, the use of supplemental feeding, types of supplemental feeding being used, use of contraception, and satisfaction with contraception.

At 8 weeks PP, participants will be emailed and requested to complete a more detailed questionnaire eliciting breastfeeding continuation, supplementation amount and type, episodes of lactation support, perception of adequate milk supply, vaginal bleeding patterns, satisfaction with breastfeeding and

contraceptive use, satisfaction with contraception, infant health and well-being, and any new pregnancies and respective pregnancy outcomes if available. Additional potential confounding factors will be explored, such as use of nipple shields, pacifiers, breastmilk expression, and other medications the participant is using. Participants will receive a gift card via text or email link for each completed survey.

Both text and email questionnaires will be sent via a hyperlink that connects to a HIPAA-compliant secure platform that will input the data directly into a REDCap database. Participants who do not have smartphones or email access will be offered participation instead using phone surveys administered by study staff and gift cards will be mailed to these participants.

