#### **Breastmilk collection and analysis:**

Women will attend an in-person visit at 4 weeks PP with their infant. Participants will have the option to collect a mid-feeding sample at home with all pumping materials and instructions sent to her home or collect a sterile sample at the visit using a study-provided breast pump. 10 mLs of breastmilk from the collection (either refrigerated sample brought to the visit or collected on-site) will be frozen at the site of the visit at the research site. The milk samples will be frozen at -80 degrees onsite. The lab will use liquid chromatography to assess the composition of breast milk and compare the concentrations of total fat, total protein and carbohydrates including oligosaccharides.

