#### 8.3.4 TIME PERIOD AND FREQUENCY FOR EVENT ASSESSMENT AND FOLLOW-UP

The occurrence of an adverse event (AE) or serious adverse event (SAE) may come to the attention of study personnel during study visits and interviews of a study participant presenting for medical care, by communication from the participant to the study team, or upon review by a study monitor.

All AEs including local and systemic reactions not meeting the criteria for SAEs will be captured. Information to be collected includes event description, time of onset, clinician's assessment of severity, relationship to study product (assessed only by those with the training and authority to make a diagnosis), and time of resolution/stabilization of the event. All AEs occurring while on study must be documented appropriately regardless of relationship. All AEs will be followed to adequate resolution.

Any medical condition that is present at the time that the participant is screened will be considered as baseline and not reported as an AE. However, if the study participant's condition deteriorates at any time during the study, it will be recorded as an AE. Changes in the severity of an AE will be documented to allow an assessment of the duration of the event at each level of severity to be performed. AEs characterized as intermittent require documentation of onset and duration of each episode.

At each study visit, the investigator will inquire about the occurrence of AE/SAEs since the last visit. Events will be followed for outcome information until resolution or stabilization.

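### After the week-4 visit no structured adverse-event inquiry is clearly specified in any arm, and all of Group 3's drospirenone exposure falls after that visit

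*Combined protocol and SAP*

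**What the plan says.** On AE capture, Section 8.3.4 gives one active route: "At each study visit, the investigator will inquire about the occurrence of AE/SAEs since the last visit". Its other routes depend on the participant seeking care, or come "by communication from the participant to the study team, or upon review by a study monitor". Section 9.4.4 puts it more passively: "AEs and SAEs will be recorded by the study team when they become aware".

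On contacts, Section 8.1 (Breastmilk collection and analysis) states: "Women will attend an in-person visit at 4 weeks PP with their infant". No other in-person follow-up visit is described. Weeks 2, 3, 5, 6 and 7 are text-link surveys. For week 8, Section 8.1 (Surveys) states: "Participants will receive an emailed hyperlink at the end of week 8 which will lead to a longer questionnaire". The topics listed for the weekly surveys are feeding and contraception. The week-8 list adds bleeding, the infant's health and new pregnancies. Neither list has a general AE question. Section 4.2, however, refers to the 8-week contact as the participant's last visit.

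On treatment, Section 8.1 (Randomization) assigns Group 3 to "placebo for 28 days followed by d-POPs initiated at 4 weeks". Its first 28-day pack is placebo only, and the packs are taken in the order dispensed.

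On output, Section 9.4.4 promises that AEs leading to discontinuation and "serious treatment-emergent AEs will be presented in a table". Section 8.3.4 says that non-serious AEs are captured as well. The synopsis (Section 1.1) sets out to explore whether pill type and timing are "acceptable to the user with minimal side effects".

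**The concern.** Group 3 is the only delayed-initiation arm, so what the trial learns about side effects of delayed drospirenone must come from Group 3's second pack. That pack begins after the only visit at which the procedures clearly place an investigator asking about AEs. Acne, which Section 2.2 names as a difference between the two progestins, is not in the Section 3 outcomes or the listed survey topics, so after week 4 it would surface only if a woman raised it herself.

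The planned table adds to the problem. With 10 women per arm, the events most likely to occur are non-serious ones that do not stop treatment, and no table of those is promised. Nor does Section 9.4.4 say from which capsule an event counts as treatment-emergent in an arm that begins on placebo. A placebo-period event could therefore be counted against delayed drospirenone.

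**Working it through.** **Inputs from the documents.** First capsule at 120-160 h after delivery (Section 6.1) or 120-168 h (Section 8.1), so day 5 to day 7. Two 28-day packs. A drospirenone pack has 24 active and 4 inactive tablets; a norethindrone pack has 28 active. Ten women per arm.

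**Assumptions.** Full adherence; week-4 visit on day 28 (no window is stated); follow-up to day 56. I count days before day 28 and before day 56. Including day 56 itself gives 22-24 active days in Group 3 instead of 21-23.

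**Step 1: the plan's own start date.** Section 8.1 gives Group 3's drospirenone start as day 28-35. First capsule plus 28 placebo days gives:
- 120 h: 5.0 + 28 = day 33.0
- 160 h: 6.7 + 28 = day 34.7
- 168 h: 7.0 + 28 = day 35.0

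The upper end of the stated window is reproduced; the lower end is not.

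**Step 2: active days, with the first capsule on day s (5 or 7).**
- Before day 28, Groups 1 and 2: 28 - s = 23 or 21. Group 3: 0.
- Before day 56, Group 1: 24 + (56 - s - 28) = 47 or 45.
- Before day 56, Group 2: 56 - s = 51 or 49.
- Before day 56, Group 3: 56 - s - 28 = 23 or 21.

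| | Active days before day 28 | Active days before day 56 | Share |
|---|---|---|---|
| Group 1 | 21-23 | 45-47 | 21/45 = 47% to 23/47 = 49% |
| Group 2 | 21-23 | 49-51 | 21/49 = 43% to 23/51 = 45% |
| Group 3 | 0 | 21-23 | 0% |

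**Step 3: sensitivity to the visit and start dates.** Section 7.3 has a missed visit rescheduled within one week; take that as day 35 at the latest. Group 3 then has 35 - 33 = 2 of 23 active days (9%) before the visit if s = 5, and 0 of 21 if s = 7. If drospirenone instead began on day 28, the lower end of the stated window, all 24 active days would fall on days 28-51. Then 0 of 24 precede a day-28 visit, and 35 - 28 = 7 of 24 (29%) precede a day-35 visit.

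**Step 4: what weaker capture could cost (illustration only).** The documents give no AE rate and no capture rate. For true risk p, capture fraction c and n = 10, the probability of recording at least one event is 1 - (1 - pc)^10.

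| True risk p | c = 100% | c = 70% | c = 50% | c = 30% |
|---|---|---|---|---|
| 10% | 0.65 | 0.52 | 0.40 | 0.26 |
| 20% | 0.89 | 0.78 | 0.65 | 0.46 |
| 30% | 0.97 | 0.91 | 0.80 | 0.61 |

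**Step 5: after the change.** An AE question at week 8 covering the time since the last contact brings the share of active days covered to 100% in every arm, for women who answer it.

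**The case against.** A reader might infer that harms of delayed drospirenone are never asked about. The documents do not support that. Section 4.2 calls week 8 a visit, and read with Section 8.3.4 that would require an AE inquiry after nearly all of Group 3's exposure. The week-8 questionnaire asks about bleeding, a central side effect of these pills, and about the infant's health and new pregnancies. Section 8.1 also only summarises survey topics; the instruments are not in the documents, so an AE item could exist. These points stand. They make the defect an unresolved contradiction, not a proven absence: an emailed link is not an investigator's inquiry, and nothing connects the week-8 answers to AE recording or to the safety table.

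A reader might also infer that ascertainment is unequal between arms. It is not: the blinded arms share one contact schedule, and up to week 4 the comparison of active drug with placebo is the one the design intends. The lack of clear inquiry during the second pack affects all three arms. Only the share of on-drug time covered differs, and no between-arm safety test is planned.

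Finally, this is a 30-woman feasibility pilot (Section 9.2), none of its numbered aims is a general AE aim, all AEs are reported to the IRB (Section 8.3.5), and Section 9.4.4 does not forbid further listings. That limits the weight of the point. It does not answer it, because the synopsis raises side effects by timing and the remedy is cheap.

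**Conclusion.** The point holds in a limited form. Following the procedures as written leaves Group 3's whole active period, 21-23 days before day 56, to spontaneous report plus a few specific week-8 items, while 43-49% of active days in the early-start arms precede a direct inquiry. Two things suffer: the description of harms under delayed drospirenone, and any whole-study comparison of Groups 1 and 3. The week-4 contrast does not.

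The 0% rests on a day-28 visit and capsules taken as dispensed. It rises to at most 9% with a day-35 visit, or 29% if the start were also day 28. It would cease to matter if week 8 is in fact conducted as a visit with AE inquiry, which the documents leave open. Separately, the promised table omits non-serious AEs that do not lead to discontinuation and does not separate Group 3's placebo and drospirenone periods. This should be corrected, but it does not threaten the primary analysis.

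**What to change.** 1. Reconcile Sections 4.2, 8.1 (Surveys) and 8.3.4: state whether week 8 is a study visit, and who asks about AEs and how.
2. Add the same brief AE question, one for the mother and one for the infant, to the existing surveys (at least weeks 5 to 8) and to the week-4 visit, in all arms, with staff follow-up of any positive answer.
3. In Section 9.4.4, tabulate all AEs by arm, for mother and infant separately, split at the start of the second pack, and define treatment-emergent for an arm that begins on placebo. Record the date of the first second-pack capsule if it is not already collected, since the split depends on it.
4. Separately, reconcile the stated day 28-35 drospirenone start with 28 placebo days begun on day 5-7, the two first-capsule windows (120-160 h and 120-168 h), and the Section 8.1 counselling text that relies on day 33.

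The cost is two items in forms already being sent, possibly one date field, and one more descriptive table. The downside is a few more minor AEs to record and follow. Cells will be sparse at 10 per arm, so the table should be read as description only.
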